8.2.13. Pregnancy

Pregnancy per se is not an AE except for the cases when it is reasonable to suppose that administration of the study product reduced efficacy of contraceptive methods. Congenital abnormalities or birth defects in children of study subjects are considered to be SAEs. Elective abortions, abortions for medical reasons, with sequelae as well as any serious pregnancy complications (including spontaneous abortions) should be recorded as SAEs. Planned abortions without sequelae are not AEs.

All pregnancy cases reported during the study (including pregnancies of female partners of the study subjects) should be duly recorded. Where pregnancy is confirmed, the investigator should notify Sponsor pharmacovigilance officer by submitting a pregnancy report. Pregnancy report should be filled by authorized employee of the study site within 24 hours after obtaining pregnancy information. A pregnancy should be reported by filling out the "Pregnancy" page in the eCRF within 24 hours by an authorized study site employee from the time the information about pregnancy becomes available. If access to the eCRF is temporarily impossible, the center has the opportunity to report the pregnancy by sending a scan of the hard copy of the Pregnancy Report Form by email to:

[contact]

or by [contact]

Further Sponsor should be provided with the information on the pregnancy outcome. Pregnancy of the study subjects and partners of male study subjects will be recorded since the study product administration until the last study-related procedure.

Outcome of each pregnancy (spontaneous abortion, elective abortion or for medical reasons, normal delivery or delivery of a child with congenital abnormalities or birth defects) should be recorded even if the study subject withdrew from the study. Infant's health status should be monitored where possible until 6 weeks, 6 months and 1 year old.

8.2.14. Other safety reports

Investigators will submit to LEC/IRB reports on other treatment safety aspects subject to immediate notification if they affect risk-benefit ratio, related to the treatment or may require relevant changes in the treatment within the study or study methodology.

In addition to urgent reports, Sponsor will annually prepare safety update reports on RPH-104 containing all the new relevant safety information obtained during the reporting interval. Summary of these reports will be sent to the investigators for submission to LEC/IRB of medical institutions on an annual basis.

9. Statistics

9.1. General provisions

Detailed description of statistical data analysis including last observation carried forward will be presented in statistical analysis plan (SAP). SAP development will be finalized until the study database lock. Any deviations from analysis planned in SAP should be justified in the clinical study report.

Any data will be generalized using descriptive statistics: number of the subjects, mean value, minimum and maximum, median and quartiles for continuous variables, frequency of observations with percentages - for qualitative variables.

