	
review. This set is supplementary population for efficacy assessment.
 
Safety Population:
 
All randomized subjects, who received the study products.
 
General considerations:
 
Detailed description of statistical data analysis including last observation carried forward will be presented in statistical analysis plan (SAP). SAP development will be finalized until the study database lock. Any deviations from analysis planned in SAP should be justified in the report on study results.
 
Any data will be generalized using descriptive statistics: number of the subjects, mean value, minimum and maximum, median and quartiles for continuous variables, frequency of observations with percentages - for qualitative variables.
 
After the last subject completes 28-day follow-up period, an analysis of hsCRP, BNP and NT-pro-BNP will be performed for 14 and 28 days of the study. The analysis results may be used to define the strategy for further RPH-104 development.
 
At this stage the primary efficacy analysis will be performed. This analysis will be performed only once and will not be repeated during the final analysis stage. Sensitivity analysis cannot be done during the interim stage and will be performed during the final analysis stage.
 
Secondary efficacy variables (AUC from day 1 to day 28) will be derived and analysed for parameters hsCRP, BNP and NT-pro-BNP at the interim analysis stage. This analysis will be performed only once and will not be repeated during the final analysis stage.
 
After the completion of the study, a final statistical data analysis will be conducted, and the final study report will be prepared.

--	---

Table 1. Schedule of visits and procedures

Time point/Study procedures	Day 1	Day 3 ¹	Day 14±3	Day 28±3 /Early withdrawal visit (from Day 1 till Day 28)	Month 6 ² ±2 weeks	Month 12 ±2 weeks /Early withdrawal visit (from Day 29 till Day 365)
Visit	1	2	3	4	5	6
Informed consent	X					
Evaluation of inclusion/exclusion criteria	X					
Medical history	X					
Recording previous therapy	X					
Demographic data	X					
Recording 12-lead ECG results ³	X					
Recording CAG findings ⁴	X					
Randomization	X					
Administration of the study product ⁵	X					
Urine pregnancy test for females with childbearing potential (test strips)	X					
Hematology ⁶	X					
Efficacy evaluation						
Blood sampling for measuring hsCRP, BNP, NT-pro-BNP	X	X	X	X		X ⁷
Outcome registration		X	X	X	X	X

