9.7. Interim analysis

After the last subject completes 28-day follow-up period, an interim analysis of hsCRP, BNP and NT-pro-BNP will be performed after 14 and 28 days of the study. Based on this analysis, decision on the study termination will not be taken. The analysis results may be used to define the strategy for further RPH-104 development.

Population for performing an interim analysis – Full Analysis Set.

During the interim analysis the primary efficacy analysis will be performed (see section 9.3.3.1). This analysis will be performed only once and will not be repeated during the final analysis stage. Sensitivity analysis can't be done during the interim stage and will be performed during the final analysis stage.

Secondary efficacy variables (AUC from day 1 to day 28) will be derived and analysed for parameters hsCRP, BNP and NT-pro-BNP at the interim analysis stage (see section 9.3.3.2). This analysis will be performed only once and will not be repeated during the final analysis stage.

Values at visits (Day 1 – baseline, Days 3, 14 and 28) and changes from baseline (Days 3, 14 and 28) will be described for hsCRP, BNP and NT-pro-BNP parameters using descriptive statistics supported with graphics.

All individual subject's data will be kept blinded for the Sponsor and all other staff involved into the data review except unblinded statistician.

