12.4. Database management and quality control

In the studies using eCRFs the Sponsor (or appointed CRO) representatives will analyze the data entered by the site personnel for accuracy and completeness. In case of discrepancies or missing values, queries for data will be generated specifying the nature of the issue and required clarification. These queries will be forwarded to the study site. The appointed study site officer is required to provide responses to the queries and make any necessary amendments immediately.

By the end of the study, any Protocol deviations will be determined. By the end of these actions and confirmation of database completeness and accuracy, it will be locked and prepared for data analysis.

After database lock, the Investigator will receive a CD or paper version of subject data for archiving in the study site.

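### The primary analysis is run once at the Day-28 cut, but the SAP need only be final by an end-of-study lock about 11 months later, so the unnamed sensitivity analyses and some 12-month BNP/NT-pro-BNP model detail could be settled with group results known

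*Combined protocol and SAP*

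**What the plan says.** Section 9.1 refers the detailed analysis description to the SAP and gives its deadline: "SAP development will be finalized until the study database lock". The protocol summary says the same. Section 12.4 describes one lock. It follows the determination of protocol deviations at the end of the study: "By the end of these actions and confirmation of database completeness and accuracy, it will be locked and prepared for data analysis".

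Section 9.7 places an analysis after the last subject has completed Day 28. Its population is stated: "Population for performing an interim analysis – Full Analysis Set". It includes the main test: "During the interim analysis the primary efficacy analysis will be performed (see section 9.3.3.1"). The Day 1-28 AUCs of hsCRP, BNP and NT-pro-BNP are analysed at the same point. Each of these analyses is done once and not repeated. In addition, visit values and "changes from baseline (Days 3, 14 and 28) will be described for hsCRP, BNP and NT-pro-BNP parameters using descriptive statistics supported with graphics".

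The sensitivity analyses are postponed. In the summary's words: "Sensitivity analysis cannot be done during the interim stage and will be performed during the final analysis stage". Neither the summary nor section 9.7 names any of them.

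On use and access, section 9.7 says: "The analysis results may be used to define the strategy for further RPH-104 development". For individual subjects, "data will be kept blinded for the Sponsor and all other staff involved into the data review except unblinded statistician". It does not say who receives the group-level results.

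The two descriptions of the Per Protocol Set time the blinded deviation review differently. The summary puts it before database lock; section 9.2 puts it before the blind is broken.

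**The concern.** A SAP protects an analysis only if it is signed before the people who write it can know the result. Here the treatment comparison on the primary endpoint comes first, and the stated SAP deadline comes months later. If the SAP is still open at Day 28, as the deadline allows, a sensitivity analysis of the primary endpoint could be chosen by someone who knows how each dose compared with placebo. The same holds for unspecified features of the 12-month BNP/NT-pro-BNP model, because most of the data behind that endpoint will already have been summarised.

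What is at stake is the credibility of the supporting evidence. Section 2.4 says that the choice between 80 mg and 160 mg for later phases will rest on this trial's data, and section 9.7 lets the Day-28 results inform development strategy. Sensitivity analyses are there to show whether the hsCRP result is robust. If the report cannot show that they were set before unblinding, they serve that purpose poorly.

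**Working it through.** **1. The plan's own figures, to check that the fix leaves them alone.** Section 9.4 gives 34 per arm, a standardised effect of 0.80 and two-sided alpha 0.05, with power above 90%.
- Normal approximation: power = Φ(d√(n/2) − 1.96) = Φ(0.80 × √17 − 1.96) = Φ(1.34) = 0.910. The noncentral t gives 0.902.
- After 20% loss: 34 × 0.8 = 27.2, taken as 27 per arm. This gives 0.836 (normal) and 0.822 (t), against the stated value above 80%.
- Screening: 102 / 0.70 = 145.7, so 146.

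All three reproduce. None depends on when the SAP is signed.

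**2. Length of the gap.** Inputs are Visit 4 at Day 28 ± 3 days and Visit 6 at Day 365 ± 14 days (Table 1; sections 4.3.4.4 and 4.3.4.6), with 30.44 days per month.
- Nominal: 365 − 28 = 337 days = 11.1 months.
- Shortest: (365 − 14) − (28 + 3) = 351 − 31 = 320 days = 10.5 months.
- Longest: (365 + 14) − (28 − 3) = 379 − 25 = 354 days = 11.6 months.

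These run from the last subject's Day 28 to that subject's last visit. Lock comes later, by a time the protocol does not give. The summary's calendar (9 months' recruitment, 22-month clinical part) would give 22 − (9 + 28/30.44) = 22 − 9.9 = 12.1 months. That assumes the clinical part is counted from first enrolment, which is not stated, so I do not rely on it.

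**3. What is still open when the group results exist.**

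| Item | Where | Fixed before the Day-28 result? |
|---|---|---|
| Primary test: Full Analysis Set, trapezoidal AUC, ANOVA, two-sided 5% | 9.2, 9.3.3.1, 9.5, 9.7 | Yes, in the protocol, and run once |
| Missing-data rule for the once-only AUCs | 9.1, referred to the SAP | In effect yes: it must be applied before there is a result |
| Sensitivity analyses of the primary endpoint | Summary, 9.7 | No: unnamed and deferred |
| 12-month BNP/NT-pro-BNP mixed model | 9.3.3.2 | Partly: baseline, group and a by-visit comparison are given; covariance, for example, is not |
| Echo-CG parameters | 7.2, referred to the SAP | Not in the protocol text, but no Echo-CG result is produced at Day 28 |
| Methods for the interaction with angiography findings | 9.3.3.3, referred to the SAP | Not in the protocol text, but not analysed at Day 28 |

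**4. How much of the 12-month BNP/NT-pro-BNP data is already seen.** Post-baseline samples are at Days 3, 14, 28 and Month 12 (Table 1; section 7.2), which makes 4. The first 3 enter the Day 1-28 AUC comparison and are described at the Day-28 analysis. 3/4 = 75%; only Month 12 is unseen.

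**The case against.** The strongest reply is that the deadline is a latest date, not a plan. The supplied text holds no separate SAP with a signing date, and section 7.2 refers to its Echo-CG content in the present tense, so the SAP may have been finished early. This stands as to fact: nothing shows that the SAP was or will be late. It does not remove the gap in the rule.

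A second reply is that the protocol may treat database lock and breaking the blind as one event, since the summary and section 9.2 use one phrase each for the same review. The SAP deadline would then precede unblinding. Section 12.4 is general and does not rule out an interim lock. But no such lock is described, and the one that is described follows an end-of-study review. The ambiguity is itself a reason to reword.

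Third, this is an exploratory phase 2a trial with no stopping decision at Day 28, and departures from the SAP must be justified in the report. That lowers the stakes, but it does not make late choice of robustness analyses harmless.

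Some stronger readings are tempting but unsupported:
- That the primary test's error rate is inflated. Its method, population and level are in the protocol, and it is run once.
- That the Per Protocol Set can be chosen after unblinding. Section 9.2 most naturally forbids it; only the summary's phrase would allow it.
- That the missing-data rule for the AUCs can be picked to suit the result. It has to be used to obtain the result.
- That Echo-CG parameters can be picked to favour a dose. Group biomarker means do not show which parameter would do so, so that exposure is indirect.
- That the data transformation is equally exposed. Section 9.3.3.2 ties it to non-normality, not to the treatment effect. Its missing criterion is a separate matter.
- That the sponsor will see the group results. The strategic use suggests it, but recipients are not named.

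**Conclusion.** The concern holds in a limited form. As written, the SAP may be finalised about 11 months after the only group comparison on the primary endpoint: 337 days nominal and 320 to 354 with windows to the last visit, with lock later still. Eleven months is a nominal figure, not a floor, since the windows allow about 10.5 months to the last visit.

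The main exposure is the sensitivity analyses of the primary endpoint, with remaining detail of the 12-month BNP/NT-pro-BNP model second. The main analysis itself is protected. No bias or type I error figure is given, because the documents do not support one.

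The conclusion assumes that the lock in section 12.4 is the one meant in section 9.1. It also assumes that group results could reach someone who can still shape the SAP; the protocol keeps only individual data blinded and does not exclude this. The point should be fixed, but it does not undermine the primary test.

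**What to change.** In section 9.1 and the summary, replace the SAP deadline with wording such as: *The SAP, including all sensitivity analyses and the 12-month BNP/NT-pro-BNP model, will be signed, and the Day 1-28 hsCRP, BNP and NT-pro-BNP data locked, before any unblinding for the Day-28 analysis.*

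Align the summary's sentence on the Per Protocol Set with section 9.2 by naming the Day-28 unblinding in both. The sensitivity analyses may still be run at the final stage, as now planned.

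The cost is SAP sign-off and the blinded review done before the Day-28 analysis instead of near study end, plus one partial data lock that the protocol does not now describe. No extra data are needed, and sample size, power and alpha stay as they are.

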9.2. Selection of data for the analysis

Statistical analysis will be conducted in the following study sets:

Full analysis set (FAS) for the efficacy analysis

Full analysis set (FAS) for efficacy analysis will include all randomized subjects who received the study products and underwent at least one hsCRP measurement after administration of the study products. This set is the main population for efficacy assessment.

Per Protocol Set (PPS)

ProtocolAll FAS subjects without important Protocol deviations affecting assessment of the primary efficacy parameter. Such Protocol deviations will be defined before breaking the blind in a blinded data review. This set is supplementary population for efficacy assessment.

Safety set

All randomized patients who have received the study drugs.

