4.3.4.2. Visit 2 (Day 3)

The following procedures will be carried out at the visit:

- blood sampling for measuring hsCRP, BNP and NT-pro-BNP;
- outcome registration;
- evaluation of vital signs (BP, HR, RR, body temperature);
- body weight measurement (for subjects who did not undergo measurement on Day 1);
- physical examination;
- recording AE and SAE;
- recording concomitant therapy.

For patients discharged on Day 2, the procedures of the Day 3 visit can be carried out ahead of schedule (on Day 2).

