5.4.5. Follow-up of withdrawn subjects

Follow-up of the subjects withdrawn due to a SAE will be performed until its resolution or stabilization.

The subjects withdrawn for other reasons will not be followed.

6. Treatment of the study subjects

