7.1. List of efficacy parameters

Primary endpoint

1. hsCRP area under curve (AUC) from Day 1 (baseline) until Day 14 [Visit 1 Day 1 – Visit 3 Day 14].

Secondary endpoints

1. hsCRP area under curve (AUC) from Day 1 baseline) until Day 28 [Visit 1 Day 1 – Visit 4 Day 28].
2. BNP area under curve (AUC) from Day 1 (baseline) until Day 28 [Visit 1 Day 1 – Visit 4 Day 28].
3. NT-pro-BNP area under curve (AUC) from Day 1 (baseline) until Day 28 [Visit 1 Day 1 – Visit 4 Day 28].
4. Incidence of fatal outcomes (cardiac and non-cardiac) during 12-month follow-up period [Visit 1 Day 1 – Visit 6 Day 365].
5. Incidence of hospitalizations due to HF or other cardiac reasons not associated with HF, or due to non-cardiac reasons during 12-month follow-up period [Visit 1 Day 1 – Visit 6 Day 365].
6. Incidence of new cases of HF (defined as hospitalization due to HF or new onset of HF) during 12-month follow-up period [Visit 1 Day 1 – Visit 6 Day 365].
7. Incidence of “fatal outcome (due to any reason) or hospitalization due to HF or new onset of HF” Frequency of fatal outcomes for any cause OR hospitalization for HF OR the development of HF in the outpatient settingsduring 12-month follow-up period [Visit 1 Day 1 – Visit 6 Day 365].
8. Incidence of “fatal outcome (due to any reason) or hospitalization due to HF” during 12-month follow-up period [Visit 1 Day 1 – Visit 6 Day 365].

- 9. 9. Changes in levels of BNP and NT-pro-BNP during 12-month follow-up period compared to baseline [Visit 1 Day 1 – Visit 6 Day 365].
- 10. Changes in structural and functional echocardiographic parameters after 12 months compared to baseline [Visit 1 Day 1 – Visit 6 Day 365].

Exploratory endpoints

- 1. Changes in concomitant therapy [Visit 1 Day 1 – Visit 6 Day 365].
- 2. Interaction between STEMI outcomes and peculiarities of coronary bed lesion based on baseline CAG results [Visit 1 Day 1 – Visit 6 Day 365].

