The number and proportions of subjects (of the number of FAS subjects and valid %) with fatal outcomes, subjects with hospitalizations and subjects with new cases of HF will be presented by treatment groups. Intergroup comparisons will be performed using exact Fisher's test.

- Changes in levels of brain natriuretic peptide (BNP, NT-pro-BNP) during 12-month follow-up period compared to baseline [Visit 1 Day 1 – Visit 6 Day 365].

Changes in BNP, NT-pro-BNP levels will be presented by descriptive statistics by the study visits and treatment groups. Changes relative to baseline will be calculated for each visit.

Comparison of changes between the treatment groups after the treatment initiation, as well as the comparison of mean changes in BNP, NT-pro-BNP levels by Visits will be performed using a basic linear mixed model with the inclusion of the baseline as a covariate and the therapy group as a factor.

CONFIDENTIAL

Translation dated 27-Oct-2021

based on Russian Version 4.0 dated 02-Oct-2021

Page 64 of 98

- Changes in structural and functional echocardiographic parameters after 12 months from the baseline [Visit 1 Day 1 - Visit 6 Day 365].

The parameters will be analyzed similar to the analysis of changes in brain natriuretic peptide level described above.

In case of significant deviations from the normal data distribution, data transformation (logarithmic or other) can be used. In case of using transformations, the relevant descriptive statistics will also include a geometric mean value.

9.3.3.3. *Analysis of exploratory endpoints*

- Changes in concomitant therapy [Visit 1 Day 1 – Visit 6 Day 365].

Number and proportion of subjects (of the number of FAS-subjects and valid %) with changes in the prescribed concomitant therapy with their causes will be presented by treatment groups.

- Interaction between STEMI outcomes and peculiarities of coronary bed lesion based on baseline CAG results [Visit 1 Day 1 – Visit 6 Day 365].

Detailed description of assessment methods will be presented in the SAP.

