9.3.4. Safety analysis

Safety analysis will be carried out on safety set.

Scope of application will be presented specifying the following variables: the number of subjects receiving RPH-104 80 mg, the number of subjects receiving RPH-104 160 mg and the number of subjects receiving placebo.

AEs will be coded using Medical Dictionary for Regulatory Activities (MedDRA). The number and percentage of the subjects with AE/SAE, overall number and percentage of recorded AE/SAE, the number and percentage of AE/SAE resulting in early withdrawal will be presented by system organ class, preferred terms and treatment groups. The data will also be generalized by the number and percentage of AEs/SAEs with various categories of causality, expectedness and severity. All AEs will be additionally presented as listings.

Quantitative safety laboratory parameters will be presented using descriptive statistics by visits and treatment groups. Changes relative to baseline and abnormal laboratory values will also be provided. The data on the number of subjects with abnormal laboratory values will be generalized for the whole study period, by visits and treatment groups. All laboratory findings will be presented as lists.

Vital signs will be presented using descriptive statistics by visits and treatment groups. Changes relative to baseline will also be presented.

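### The hsCRP-based Full Analysis Set is also the denominator for death, hospitalization and heart failure, so a subject who dies before any post-dose sample drops out of the mortality endpoint

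*Combined protocol and SAP*

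**What the plan says.** Section 9.2 admits to the FAS "all randomized subjects who received the study products and underwent at least one hsCRP measurement after administration of the study products" and adds: "This set is the main population for efficacy assessment". The same section defines a Safety set of all randomized and dosed subjects, with no sampling condition. Section 9.3.4 assigns that set to safety only: "Safety analysis will be carried out on safety set".

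For the clinical outcomes, Section 9.3.3.2 names the denominator directly: "The number and proportions of subjects (of the number of FAS subjects and valid %) with fatal outcomes", and likewise for hospitalizations and new HF. It continues: "Intergroup comparisons will be performed using exact Fisher's test".

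The mortality endpoint in Section 7.1 reads "Incidence of fatal outcomes (cardiac and non-cardiac) during 12-month follow-up period [Visit 1 Day 1" and runs to Day 365; endpoints 5 to 8 share that window. Section 7.2 places the hsCRP samples at baseline on Day 1, then Day 3, Day 14±3 and Day 28±3. Section 4.3.4.2 allows one earlier sample: "For patients discharged on Day 2, the procedures of the Day 3 visit can be carried out ahead of schedule (on Day 2").

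Section 9.1 leaves detailed methods to the SAP. Nothing in the supplied text gives endpoints 4 to 8 a different population.

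**The concern.** Requiring a post-dose hsCRP value makes sense for the hsCRP AUC, which cannot be computed without one. It does not make sense for death. Giving a blood sample after dosing requires surviving to give it, so membership of the set depends on a post-randomization event that can be the endpoint itself. The deaths removed are the earliest ones.

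The two composites that include death lose the same subjects. Early HF can be lost too: the footnote to Section 7.2 counts HF arising within 24 hours of admission as an HF hospitalization when it prolongs the index stay, and that event disappears if no post-dose sample follows.

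Objective 3, clinical outcomes within 12 months, rests on endpoints 4 to 8. Section 9.8 sets up a blinded independent committee whose classification of these events is final. Leaving adjudicated early deaths out of the efficacy table would undercut that work, and the report could show two different death counts per arm. Section 2.4 says dose selection for later phases will use this study's risk-benefit data, so an understated death count in one arm would matter beyond the table.

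**Working it through.** **The plan's own figures.** The concern rests on no stated figure, but the sample size in Section 9.4 was reproduced to fix the denominators. With 34 per arm, standardized effect 0.80 and two-sided alpha 0.05, normal-approximation power is Φ(0.80 × √(34/2) − 1.96) = Φ(1.338) = 0.910; the t-test gives 0.902. Both exceed the stated 90%. After 20% loss (27 per arm) the values are 0.836 and 0.822, above the stated 80%. Screening: 102 / 0.70 = 145.7, so 146. None of this is affected by the concern.

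**Who is lost.**

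| Dosed subject | Post-dose hsCRP? | Endpoints 4–8 (FAS) | Safety tables |
|---|---|---|---|
| Dies before any post-dose sample | No | Absent from numerator and denominator | Counted |
| Leaves alive and gives no later sample | No | Absent from numerator and denominator | Counted |
| Misses Day 3, sampled at Day 14, Day 28 or an early withdrawal visit by Day 28 | Yes | Counted | Counted |
| Sampled on Day 3, dies later | Yes | Counted | Counted |

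An early withdrawal visit (Section 4.3.4.8) can keep a living subject in the set. It cannot keep one who has died.

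**How many.** The documents give no mortality between dosing and first sample. Let q be that probability (an assumption) and n = 102. Expected losses = n × q; chance of at least one = 1 − (1 − q)^102.

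| q (assumed) | Expected deaths lost | Chance of at least one |
|---|---|---|
| 0.1% | 0.1 | 10% |
| 0.2% | 0.2 | 18% |
| 0.5% | 0.5 | 40% |
| 1% | 1.0 | 64% |
| 2% | 2.0 | 87% |

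**What one death is worth.** 1/34 = 2.9 percentage points. Section 2.1 cites 12-month mortality of about 10% from a European register. Used for scale only, that gives 34 × 0.10 = 3.4 deaths per arm, so one lost death is 1/3.4 = 29% of an arm's expected count.

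**Effect on reported results (hypothetical counts).**

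- Three deaths in one arm, one unsampled: 3/34 = 8.82% becomes 2/33 = 6.06%, a drop of 2.76 points. Two-sided Fisher test against 0/34: p = 0.239 both ways.
- Two later deaths in each arm plus two unsampled deaths on active: 4/34 vs 2/34 (11.8% vs 5.9%) becomes 2/32 vs 2/34 (6.2% vs 5.9%). The visible difference all but vanishes.
- Extreme case, one unsampled death on active and six later deaths on placebo: 1/34 vs 6/34, p = 0.105, becomes 0/33 vs 6/34, p = 0.025.

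**The case against.** The best counter-argument is that the problem may never arise. Subjects have already had PCI with stenting, and Section 5.2 excludes cardiogenic shock, inotropic or mechanical support, unstable hemodynamics and pre-existing ejection fraction below 40%. The exposed interval is about two days. Set against 10% mortality at 12 months, a 2% rate would put a fifth of the year's deaths there, so the upper end of the range is generous. This stands, and it is why the lower rates are shown as well.

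The deaths are also not hidden. They appear in the safety tables and in the disposition summary of Section 9.3.1, where a reader could reconcile the counts. That is true, but the efficacy comparison would still use the incomplete count.

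The rule is the same in every arm, and median Tmax in healthy volunteers was 96 hours overall and 120 hours at 160 mg (Section 2.2). Deaths before Day 3 would therefore precede typical peak exposure, and a treatment-related distortion is not shown. That also stands. What is shown is an understated incidence, plus chance imbalance that small arms magnify. The one illustration in which significance changes needs six placebo deaths in 34 (17.6%), and these are secondary endpoints in an exploratory study without multiplicity adjustment.

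Two textual points remain. The synopsis asks for a CRP rather than an hsCRP measurement, so a local in-hospital CRP might keep some subjects in. Section 9.3.3.2 also mentions a second percentage, over valid cases, that it does not define. Neither retains a subject who dies with no post-dose measurement. Deferral to the SAP does not settle it either, because Section 9.3.3.2 has already named the FAS.

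**Conclusion.** The concern holds. Read together, Sections 9.2 and 9.3.3.2 remove from the mortality endpoint and both composites any dosed subject who dies before a post-dose hsCRP sample, and no supplied text prevents it.

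The likely count is small: between a fraction of one death and about two among 102, depending wholly on an assumed rate that the documents do not supply. If no dosed subject dies unsampled, no death is lost. If one does, that arm's reported mortality falls by nearly 3 points, against an expected level of around 10%.

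The harm is a biased incidence and inconsistent death counts between efficacy and safety tables, rather than a lost test result; at 34 per arm these comparisons are largely descriptive. The primary and other biomarker AUC analyses are unaffected. It should be fixed because the stated rule gives a wrong incidence and the correction costs almost nothing.

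**What to change.** Keep the hsCRP-based FAS for the biomarker endpoints. Analyse secondary endpoints 4 to 8 in all randomized subjects by assigned arm, counting every death recorded from randomization. The minimum acceptable alternative is the existing Safety set of all randomized and dosed subjects.

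Amend Sections 9.2 and 9.3.3.2 and carry the same population into the SAP. Do this before any unblinded analysis, including the one in Section 9.7 after the last subject's Day 28 visit. That analysis covers only hsCRP, BNP and NT-pro-BNP, but a population chosen after unblinding is harder to defend.

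The cost is wording plus one further analysis population. Outcomes already recorded need no new visits or patients. The change does not recover outcomes after withdrawal for reasons other than an SAE, because Section 5.4.5 states: "The subjects withdrawn for other reasons will not be followed".
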